### **2. Design**

This study is a randomized, double-blind, placebo-controlled trial with 16-week intervention and 18-month follow-up assessment. The design met the principles of the Declaration of *Helsinki*, and was approved by the Ethics Committee of Teaching Hospital of Chengdu University of Traditional Chinese Medicine. Then signed informed consents will be obtained from each participant.

The enrolled participants will be randomly assigned into the YZAS group or the placebo group with the allocation ratio of 1:1 using the statistical package. The unique code will be assigned to each newly enrolled participant and preserved in the trial management board. A statistician expert will act as the coder and be shielded from subject recruitment.

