### **3. Methods**

#### **3.1 Participants**

The investigators anticipate recruiting 80 participants from Teaching hospital of Chengdu University of Traditional Chinese Medicine, community, and nursing homes. All patients will undergo standard medical examination and neuropsychological testing to ensure correct diagnosis of aMCI.

The inclusion criteria are (1) subject has assigned informed consent to participate in the study and continues to give willing consent for participation; (2) age from 60 to 85 years with a diagnosis of aMCI; (3) educational level of at least 6 years; (4) availability of a "study partner" who can assist in completing rating scales for the duration of the study; (5) cognitive complaints reported by the subject and confirmed by the "study partner"; (6) clinical Dementia Rating (CDR) global score of 0.5, and memory item score of 0.5; (7) mini-mental state examination (MMSE) score of 24-30; (8) Diagnostic and Statistical Manual of Mental Disorders, Version 5 (DSM-V) criteria of dementia not fulfilled

The exclusion criteria are as follows: (1) has been previously enrolled in this study and received the investigational product; (2) has received an investigational product within 30 days prior to screening; (3) has received disease-modifying therapy; (4) has a known allergy to the study drug or any of its constituents; (5) has a history of alcohol abuse or alcohol dependency in the 3 years prior to study entry, or is an alcoholic or drug addict, as determined by the investigator; (6) has ongoing clinically significant (as judged by the investigator), metabolic or any other disease that could currently cause impaired memory (e.g., untreated thyroid disease, vitamin or other nutritional deficiencies, chronic kidney, or liver disease); (7) memory impairment that can be attributed to a disease or condition other than an early phase neurodegenerative syndrome; (8) has a parkinsonian movement disorder; (9) use of psychoactive medications that would affect the subject's ability to reliably perform neurocognitive testing or create uncertainty in distinguishing between the effects of the psychoactive medication and the subject's underlying cognitive impairment (e.g., benzodiazepines, sedatives, antipsychotics); (10) with history of major recurrent depressive disorder (DSM-V) within the last 5 years prior to screening; (11) has a brain tumor or other

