### **4.2 Statistic analysis**

Analysis will be conducted by a statistician of the National Clinical Trial Center of Chinese Medicine (Chengdu, China), who will be blinded to the whole trial and using SAS 9.2 software (Cary, NC, USA) and SPSS 19.0 software (IBM, NY, USA).

Unless otherwise specified, all mechanism, efficacy and safety analyses will be strictly conducted according to the intention-to-treat (ITT) principle and the full analysis set (FAS) population, the per-protocol set (PPS) population and the safety set (SS) population. Missing values will be replaced by the last observation carried forward (LOCF) method. ADAS-cog (including its monomial item) changes from baseline and the secondary outcomes will be assessed using an analysis of covariance with treatment groups as factors and baseline values as covariates. Standardized mean

differences will be used to express effect sizes in SD. The baseline homogeneity of the baseline characteristics between the two groups will be analyzed with Fisher's exact test, or  $\chi^2$  test for categorical measures and with the *t* test or Wilcoxon rank-sum test for continuous measures. The statistical significance is defined as a one-sided P-value of <0.05 and 95% confidence interval.

For the gut microbiome analysis, sequenced data will be interpreted using the bioinformatics tools programmed in the Ion Reporter software. QIIME algorithms will determine the bacterial diversity within a sample ( $\alpha$  diversity) and among all the samples ( $\beta$  diversity). Additionally, multivariate data analysis with principal component analysis on the diversity indexes and comparisons of genus and species level data will be performed to reveal differences in the microbial composition between individuals with normal cognition and ones with aMCI. The Benjamini–Hochberg false discovery rate adjustment will be used to account for the number of taxa tested in each comparison.

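### The primary ADAS-cog ANCOVA adjusts only for baseline score; pre-specifying age and education (and setting, if recorded) would add modest precision and direct protection against chance imbalance

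*Combined protocol and SAP*

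**What the plan says.** - **Model.** Section 4.2 assesses ADAS-cog change and the secondary outcomes by "analysis of covariance with treatment groups as factors and baseline values as covariates". In context, the baseline values are those of the outcome being analysed. No further covariate and no covariate sensitivity analysis is named.
- **Baseline comparison.** The same section states that "The baseline homogeneity of the baseline characteristics between the two groups will be analyzed with Fisher's exact test" or other standard tests. It does not say what follows if the groups differ.
- **Allocation.** Under section 2, participants are "randomly assigned into the YZAS group or the placebo group with the allocation ratio of 1:1 using the statistical package". Stratification, blocking and minimization are not mentioned.
- **Population.** Section 3.1 plans 80 participants "from Teaching hospital of Chengdu University of Traditional Chinese Medicine, community, and nursing homes". Eligibility requires "age from 60 to 85 years with a diagnosis of aMCI" and "educational level of at least 6 years". No section says that recruitment setting is recorded as a variable.

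**The concern.** Age, education and living situation plausibly relate to cognitive change beyond what the baseline ADAS-cog score captures. The sample is small, covers a 25-year age span and comes from three kinds of source. With 40 per arm, a visible chance difference in at least one of these factors is quite likely, and the stated model would not adjust for it directly.

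The homogeneity tests do not fill the gap. A significance test between randomized arms corrects nothing. With no covariates fixed in advance, it also invites choosing them after the baseline table has been seen.

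At stake are the width of the interval and the credibility of the estimate in a trial that happens to be unbalanced. The validity of the test is not at stake.

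**Working it through.** **Inputs from the documents.** 80 participants, 40 per arm; 33 evaluable in the treatment group for 90% power; maximum dropout 20% (section 4.1). One-sided 0.05, LOCF and intention-to-treat (section 4.2).

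**Assumed inputs, none of which the documents give.** Nursing-home share, size of any setting effect, and the share of residual variance (R²) explained by the added covariates after baseline score.

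**The plan's own figure.** The 33 cannot be reproduced, because no effect size or SD is stated. Inverting the usual formula gives a scale: d = (1.645 + 1.282) × √(2/33) = 0.72 SD. The 40 matches 33 × 1.20 = 39.6.

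**1. Chance imbalance in setting.** Suppose 20 of 80 come from nursing homes.
- Fixed 40:40 split, hypergeometric: P(13 v 7 or worse, either direction) = 0.196, and 0.098 in the direction of one given arm.
- Arm sizes free to vary, Binomial(20, 0.5): 0.263. Section 4.1 fixes 40 per arm, so 20% is the better figure.
- A 13 v 7 split is 6/40 = 15 percentage points. Across the assumed shares checked, from 20% to 50%, a gap of 15 points or more has probability about 16–26%, and of 20 points or more about 5–12%.

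**2. Chance imbalance in age or education.** The SE of a standardized difference is √(2/40) = 0.224. P(difference ≥ 0.3 SD) = P(|Z| ≥ 0.3/0.224 = 1.34) = 18% for each covariate. For two independent covariates, the chance that at least one reaches 0.3 SD is 1 − 0.82² = 33%.

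**3. Shift in the estimate.** Shift = gap × setting effect remaining after baseline adjustment. With a 15-point gap and an assumed effect of 0.5–1.0 SD: 0.15 × 0.5 = 0.075 SD to 0.15 × 1.0 = 0.15 SD. Against an SE of 0.224 SD, that is about 0.34 to 0.67 of one SE.

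**4. Precision.** With q covariates and N analysed, the expected SE is roughly proportional to √[(1 − R²)/(N − 3 − q)]. The baseline-only model has q = 1. Adding three covariates gives a ratio of √[(1 − R²) × 62/59] at N = 66 (twice 33) and √[(1 − R²) × 76/73] at N = 80 (all participants, as LOCF could give). Adding two gives √[(1 − R²) × 62/60] and √[(1 − R²) × 76/74].

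| Assumed R² | 3 added, N = 66 | 3 added, N = 80 | 2 added, N = 66 | 2 added, N = 80 |
|---|---|---|---|---|
| 0 | 1.025 | 1.020 | 1.016 | 1.013 |
| 0.05 | 0.999 | 0.994 | 0.991 | 0.988 |
| 0.10 | 0.973 | 0.968 | 0.964 | 0.961 |
| 0.15 | 0.945 | 0.941 | 0.937 | 0.934 |
| 0.20 | 0.917 | 0.913 | 0.909 | 0.906 |

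**5. Error rates by simulation.** 8,000 trials per scenario, 40:40, 27 of 80 from nursing homes, setting effect 0.5 SD, age and education 0.2 SD per SD each (all assumed), one-sided 0.05.

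| | Baseline only | Adjusted |
|---|---|---|
| Type I error, all trials | 5.1% | 5.2% |
| Type I error when setting favours active by ≥ 15 points (about 8% of trials) | 9.5% | 4.3% |
| Power at d = 0.72 | 95.2% | 96.7% |

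The conditional row rests on 0.0779 × 8,000 ≈ 623 trials. Its Monte Carlo SE at 9.5% is √(0.095 × 0.905/623) ≈ 1.2 points.

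**The case against.** The strongest reply is that nothing here is an error. ANCOVA on treatment and baseline score is a valid pre-specified analysis, and chance imbalance is part of the sampling variation that the p-value and interval already cover. This stands: simulated type I error is 5.1%. The 9.5% arises only after selecting the unlucky trials, under an assumed setting effect.

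A reader might infer three stronger things that the documents do not support.
- **That randomization ignores setting.** Section 2 is silent on stratification. Silence does not show that simple randomization will be used.
- **That setting data are already collected.** Age and education follow from eligibility. Recruitment from several sources does not establish that the source is recorded as a variable.
- **That an imbalance goes wholly uncorrected.** The baseline score removes whatever part acts through baseline severity, and eligibility (CDR 0.5, MMSE 24–30, at least 6 years of education) narrows the range. What is missing is direct adjustment for the remainder.

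It is also fair that every effect-driving input is assumed, that a setting effect of 0.5–1.0 SD would be large beside an implied treatment difference of 0.72 SD, and that the documents do not show how prognostic these factors are at 16 weeks or later. These points limit the size of the concern. They do not answer why two available, plausibly prognostic covariates are left out, or what the homogeneity tests are for.

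**Conclusion.** The point holds as a low-priority improvement. The model adjusts for baseline score alone, no stratification is described, and the homogeneity tests have no stated consequence, although age and education should be available.

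The planned comparison remains valid. The likely gain is modest: with three covariates, the SE is about 3% smaller at an assumed R² of 0.10 and 8–9% smaller at 0.20, roughly neutral at 0.05, and 2–2.5% larger at 0. The added benefit is protection in a particular trial with an uneven split. On an assumed 20 nursing-home residents, a gap of 15 points or more would occur in about one in five 40:40 randomizations and would move the estimate by less than one SE. Confidence in the size is low, because the documents supply neither the setting shares nor the prognostic strengths.

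**What to change.** In section 4.2, before unblinding:
- pre-specify age and years of education as additional covariates in the primary ADAS-cog ANCOVA;
- add recruitment setting (nursing home v other) if it is recorded;
- keep the baseline-only model as a sensitivity analysis;
- state that covariates will not be selected from the homogeneity tests.

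In section 2, state whether randomization is stratified, and by what.

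The cost is a few sentences, with no extra participants or visits. The statistical price is two or three degrees of freedom and an SE about 1–2.5% larger if none of the covariates is prognostic. The sponsor should first confirm that the CRF holds actual years of education and not only that the 6-year threshold was met, and whether it holds the recruitment source.

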#### **3.3.2 Secondary outcome**

Secondary measures includes the MMSE, MoCA (Changsha Version), CDR, PSQI, ADLs, and gut microbiome.

- The MMSE is an 11-question measure that tests five areas of cognitive function (orientation, registration, attention and calculation, recall, and language). The maximum score is 30 and a score below 24 is considered abnormal for dementia screening.
- The MoCA (Changsha Version) will also be used to evaluate general cognitive function, as it contains visuospatial processing and organizational capability which can make up for the shortcoming of the MMSE. The total score for it is 30, with a higher number indicating a more intact cognitive function. Meanwhile, the MoCA has been shown to be a promising tool to detect MCI and early AD.
- The CDR will be used as an assistant evaluation for patients' dementia severity, which scored 0-3, with higher scores indicating more severity. It is a semi-structured interview performed with the patient and caregiver (informant),

characterizing six domains of cognitive and functional performance. The CDR sum of boxes (CDR-SB) scored 0-18, will also be applied to assess patients' cognitive status, with higher scores indicating worse functioning.

- The Pittsburgh Sleep Quality Index (PSQI) will be used to assess participants' comprehensive quality of sleep, which involves sleep quality, sleep duration, sleep efficiency, sleep disorders, daytime dysfunction, sleeping aids, etc. The total score for it is 21, with a higher score indicating a worse sleep quality.
- ADLs will be assessed including basic activities of daily living (BADL) and instrumental activities of daily living (IADL). An individual's BADL will be evaluated mainly by the subjects' performance from the perspectives of bathing, dressing, grooming, initiation, toileting and feeding, with six items and a sum of scores ranging from 0 (normal) to 24 (complete dependence on others). And modified Lawton Instrumental Activities of Daily Living Scale will be used to measure the IADL of a subject, with eight items and a sum of scores ranging from 0 (normal) to 32 (complete dependence on others).

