These clinical tests will be administrated by a trained, certified clinician or rater experienced in the assessment of patients with cognitive deficits. And the rater who will conduct the CDR for a patient cannot complete any other rating scales for the same patient, and will be blinded to the results of all other neuropsychological scales. All the questionnaires will be assessed at baseline (before intervention), at 8 and 16 weeks (during intervention) and 6, 12, and 18 months after intervention.

- Fecal genomic DNA will be extracted from frozen stools using QIAamp DNA mini stool kit (Qiagen, Hiden, Germany), obtained from the patients with aMCI and 15-20 participants with normal cognition at baseline. After PCR amplification, DNA fragments will be sequenced on an Illumina HiSeq 2500 instrument and an Illumina HiSeq X instrument for 16SrDNA and metagenomics analyses respectively at Biomarker Technologies Co, Ltd (Beijing, China) to analyze the differences in gut microbiome between patients with aMCI and individuals with normal cognition.

When it is available, the investigators will also assess the change in gut microbiome between the treatment group and the placebo group after the intervention of YZASG in the same way.

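### Does fixing CDR global at 0.5 on entry undermine the planned ANCOVA and standardised mean difference for that score?

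*Combined protocol and SAP*

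**What the plan says.** Inclusion criterion 6 in section 3.1 requires a "clinical Dementia Rating (CDR) global score of 0.5, and memory item score of 0.5".

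Section 3.3.2 lists CDR among the secondary measures and describes two scores. The first is the global rating, "which scored 0-3, with higher scores indicating more severity". The second is the sum of boxes: "The CDR sum of boxes (CDR-SB) scored 0-18, will also be applied". On timing, the section says "All the questionnaires will be assessed at baseline (before intervention" and then lists the later visits. It does not say whether the eligibility CDR serves as the baseline CDR.

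Section 4.2 has one rule for all these scales: "the secondary outcomes will be assessed using an analysis of covariance with treatment groups as factors and baseline values as covariates". Effect sizes follow in the next sentence: standardised mean "differences will be used to express effect sizes in SD". There is no exception for CDR global, and the SD is not identified for any scale.

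**The concern.** Read together, the two sections seem to ask for something that cannot be done. If everyone starts at 0.5, there is no baseline variation to adjust for, and an effect size divided by the baseline SD would be divided by zero. Dividing by the follow-up SD avoids that, but this SD is determined by how many participants leave 0.5, so one absolute difference can give quite different standardised values.

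Two reporting errors would be at stake. A CDR global result might be called baseline-adjusted when no adjustment took place. Its standardised difference might also be read beside those of the ADAS-cog, MMSE or PSQI as if it meant the same thing.

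**Working it through.** The documents give no expected value, SD or movement rate for CDR, so there is no plan figure to reproduce. The inputs are 40 per arm (section 4.1), baseline CDR global 0.5 for all (section 3.1, taking the eligibility rating as baseline), and a one-sided 0.05 level (section 4.2). The numbers changing category are assumptions, shown as a range. Each mover is taken to go from 0.5 to 1.

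**1. The covariate.** The model is y = a + b × treatment + c × baseline. With baseline = 0.5 throughout, the third column is half the intercept column, so the 80 × 3 design matrix has rank 2. Software drops the redundant term, leaving 80 − 2 = 78 degrees of freedom. For example, with 2 v 4 of 40 worsening, the difference is −0.025 and the standard error 0.0297, both with and without the covariate.

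**2. Validity of the resulting test.** I took equal binomial movement rates in the two arms and computed the exact one-sided type I error of the two-sample t test at nominal 0.05.

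| Movement rate | 1% | 4% | 6% | 10% | 20% | 30% |
|---|---|---|---|---|---|---|
| Type I error | 0.005 | 0.049 | 0.058 | 0.054 | 0.051 | 0.049 |

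The test is conservative when almost nobody moves and close to nominal otherwise.

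**3. Which SDs exist.** The baseline SD is 0. Change is follow-up minus a constant, so within each arm the SD of change equals the SD at follow-up. The ANCOVA residual SD is then the same pooled quantity. It exists as soon as one participant changes category.

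**4. Size of the standardised difference.** When a proportion p of an arm moves up by 0.5, the sample variance is 0.25 × p(1 − p) × 40/39. The pooled SD is the square root of the mean of the two arm variances. Placebo always has 4 more participants progressing, so the raw difference is always (4/40) × 0.5 = 0.05.

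| Progressing, active v placebo | Pooled SD | 0.05 / SD |
|---|---|---|
| 0 v 4 | 0.107 | 0.47 |
| 2 v 6 | 0.150 | 0.33 |
| 4 v 8 | 0.179 | 0.28 |
| 8 v 12 | 0.218 | 0.23 |

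Adding participants who revert to 0 lowers the values further: 0.20 for 4 v 8 with 4 reverting per arm, and 0.15 for 8 v 12 with 8 per arm. Those two rows change two things at once, so they should not be set against the 0.47 as the effect of progression alone.

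**5. Interpretation.** With equal arms, t = SMD × √(40/2) = SMD × 4.47. So 0.47 corresponds to t = 2.08 and 0.23 to t = 1.03. The standardised difference is the planned test statistic on another scale. It shrinks because the same absolute gap stands against more variation. The relative effect also weakens across the rows: the placebo-to-active ratio of progressors goes from undefined (0 v 4) to 3.0, 2.0 and 1.5.

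**The case for a change.** The best argument for an amendment is that it costs a sentence or two and loses nothing. It would report ANCOVA and the standardised difference for CDR-SB only, tabulate CDR global by category, and name the SD for every scale. That would stop anyone choosing the standardiser after seeing the data. The choice can matter at low counts: for 0 v 4 progressing, the pooled SD gives 0.47, while the placebo-arm SD of 0.152 gives 0.05 / 0.152 = 0.33.

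Part of this stands. Section 4.2 names no SD for any scale, and a category table would show CDR global more clearly than a standardised difference. But the missing SD is a general omission that has little to do with CDR global. That score is if anything less ambiguous than the others, because its change, follow-up and residual SDs coincide. Comparability across scales is not a problem of CDR global alone either: entry limits the MMSE to 24–30 and fixes one of the six CDR boxes, memory, at 0.5, so CDR-SB is restricted too.

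A flat instruction to drop the adjustment could also do harm. If a separate CDR rating is made before intervention and varies, adjusting for it is useful, and the present rule already handles both cases.

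**Conclusion.** No change is needed. The gap is one that an analyst fills correctly in practice: the redundant covariate disappears without altering any number, and a zero baseline SD shows itself at once because it cannot yield a value to report. The pooled within-arm SD is the natural choice and is available once any participant changes category. If nobody does, there is no difference to standardise.

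The conclusion rests on the eligibility rating being the baseline rating. That is the natural reading, since no second rating is described; if there were one, the concern would be weaker still. The range of 0.47 to 0.23 rests on assumed counts and on one-step progression without reversion. A report that names its SD and shows CDR global by category would be good practice, but no test or conclusion in the trial depends on writing that into section 4.2.

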**April 14, 2018**

# **Efficacy Study of Yi-Zhi-An-Shen Granules for Older Adults with Amnestic Mild Cognitive Impairment**

## **Study Protocol with SAP**

### **1. Objectives**

The primary objective of this study is to evaluate the efficacy and safety of Yi-Zhi-An-Shen Granules (YZASG) in optimizing cognitive performance over time in elderly individuals with amnestic mild cognitive impairment (aMCI). Secondly, the investigators intend to assess whether YZASG can improve sleep quality among aMCI patients. Finally, participants' fecal genomic DNA will be extracted to analyze the gut microbial differences between individuals with aMCI and ones with normal cognition.

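### PCA on unspecified diversity indexes is only descriptive, and the between-sample distances are never tested, so a diffuse microbiome difference between aMCI and normal cognition could be missed

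*Combined protocol and SAP*

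**What the plan says.** The last objective in section 1 is to "analyze the gut microbial differences between individuals with aMCI and ones with normal cognition". Section 3.3.2 lists the gut microbiome among the secondary measures ("Secondary measures includes the MMSE, MoCA (Changsha Version), CDR, PSQI, ADLs, and gut microbiome"). It takes stool "obtained from the patients with aMCI and 15-20 participants with normal cognition at baseline".

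Section 4.2 sets out the analysis in three steps:
- "QIIME algorithms will determine the bacterial diversity within a sample" (alpha diversity), and also the diversity among all samples (beta diversity). No index or distance is named.
- "multivariate data analysis with principal component analysis on the diversity indexes" is planned. In the same sentence, "comparisons of genus and species level data will be performed to reveal differences in the microbial composition".
- BH adjustment is applied over the taxa tested in each comparison. Neither the taxon-level test nor the false discovery rate level is given.

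No test is named that compares the beta-diversity distances between the two groups. The general ANCOVA for secondary outcomes in section 4.2 has treatment group as factor and the baseline value as covariate. It therefore does not fit a baseline comparison of patients with people of normal cognition.

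**The concern.** Two separate weaknesses meet in this clause.

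The first is what the ordination is applied to. The usual within-sample indexes reduce a sample to a few numbers that describe how many taxa there are and how evenly they are spread, but not which taxa they are. If those are the indexes meant, two groups with different organisms but the same abundance profile would overlap completely on the plot.

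The second is that principal component analysis gives no group comparison with a p-value, whatever it is applied to. The quantity that summarises whole-community composition, the between-sample distance, is calculated and then left untested.

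The taxon-by-taxon comparisons then carry all the inference on composition, with only 15 to 20 controls. A real difference made up of many small changes may leave no single taxon significant after adjustment.

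**Working it through.** **Inputs from the documents.** The aMCI group is 80 planned (section 3.1); the number giving stool is not stated. Controls are 15 to 20 (section 3.3.2). The analysis steps are those of section 4.2. The documents give no effect size, power or sample size calculation for this comparison, so there is no stated figure to reproduce.

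**Step 1: do within-sample indexes carry taxon identity?** With relative abundances p_i, Shannon is −Σ p_i log p_i, Simpson is 1 − Σ p_i², and richness counts the taxa with p_i > 0. Each is a sum over taxa of a function of p_i alone, so reassigning the abundances to different taxa leaves it unchanged. Bray-Curtis distance between two samples, ½ Σ |p_i − q_i|, compares taxon with taxon and does change. Numerical check: after randomly relabelling the taxa, Shannon, Simpson, richness, Chao1 and evenness changed by at most about 1e-15. The mean Bray-Curtis distance between a sample and its relabelled copy was 0.63.

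**Step 2: what happens under a pure composition difference?** Assumed settings: 40 taxa, Dirichlet-multinomial counts, concentration 60, depth 5000, two pairs of taxa swapped in controls, 300 runs. Three procedures were compared at 0.05:
- a t test on the first principal component (PC1) of the within-sample indexes, which the plan does not itself specify;
- PERMANOVA on Bray-Curtis distances with 199 permutations, p = (1 + number of permutations at least as extreme)/(199 + 1);
- at least one taxon significant by Wilcoxon test with BH, that is, any ordered p_(j) ≤ 0.05·j/40.

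| Rejections, 15 / 20 controls | PC1 of indexes | PERMANOVA | Any taxon, BH |
|---|---|---|---|
| No difference | 5.7% / 2.7% | 4.0% / 3.3% | 4.7% / 4.3% |
| Two pairs swapped | 2.7% / 6.0% | 100% / 100% | 100% / 100% |

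With 300 runs the Monte Carlo standard error at 5% is √(0.05 × 0.95/300) = 1.3 points, so the PC1 results are at chance level. This effect is large, so it does not separate PERMANOVA from the taxon tests.

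**Step 3: PERMANOVA against the planned taxon tests.** Assumed: 80 v 18, 60 taxa, 200 runs.

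| Assumed difference | PERMANOVA | Any taxon, BH | PC1 of indexes |
|---|---|---|---|
| Six swapped pairs | 53% | 28% | 6% |
| Diffuse shift | 91% | 35% | 49% |
| One swapped pair | 95% | 97% | 6% |

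Relative power of the taxon tests: 28/53 = 0.53, 35/91 = 0.38, 97/95 = 1.02. Treating the two rates as independent, the first gap of 25 points has standard error √(0.53 × 0.47/200 + 0.28 × 0.72/200) = 4.7 points. The 2-point gap in the last row has √(0.95 × 0.05/200 + 0.97 × 0.03/200) = 2.0 points and is within noise.

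**Step 4: sensitivity to the assumed effect.** Assumed: 100 taxa, Dirichlet-multinomial, concentration 60, depth 5000, 300 runs, alternate taxa multiplied or divided by a factor. Results are for 15 / 20 controls.

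| Assumed difference | PERMANOVA | Any taxon, BH |
|---|---|---|
| Factor 1.15 | 39% / 58% | 7% / 14% |
| Factor 1.25 | 92% / 97% | 27% / 40% |
| Factor 1.35 | 100% / 100% | 58% / 80% |
| One taxon raised fivefold | 98% / 99% | 100% / 100% |
| No difference (200 runs) | 5.5% / 3.0% | 3.5% / 4.5% |

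A further set (80 v 18, 60 taxa) gave the same ordering. With one mid-abundance pair swapped, the taxon tests did better (94% v 81% and 100% v 91% under two settings). With six neighbouring pairs swapped, PERMANOVA did better (77% v 21% and 43% v 16%).

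**The case against.** The strongest reply is that the plan already tests composition. The sentence that contains the ordination also plans genus and species comparisons for the same purpose, with false discovery rate control. When no taxon differs, rejecting at least one taxon under BH acts as a Simes-type overall test. For a difference concentrated in a few taxa it does as well as PERMANOVA or slightly better. This stands. A reader might infer that the objective has no overall inference or would rest on a plot; the documents do not support that.

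A reader might also infer that the planned ordination cannot show composition. That goes too far. The preceding sentence in section 4.2 covers both alpha and beta diversity, so the indexes may include beta diversity, and an ordination of beta-diversity distances does carry composition. Even within-sample indexes are not always blind: PC1 rejected in 49% of runs under the diffuse shift in step 3. They miss a difference that leaves diversity unchanged.

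The missing distance-based test does not follow from the choice of ordination either. A well-specified principal coordinates plot is also descriptive. These are two separate gaps.

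Finally, this is a non-randomised baseline comparison under the last-listed objective, with no stated hypothesis or power, and the documents do not commit to a confirmatory overall test. That limits the importance of the point. It does not remove the ambiguity or the unused distances.

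**Conclusion.** The point holds in a limited form. The clause does not say which indexes are ordinated. If they are within-sample indexes, the ordination can miss a composition difference; that part is algebra and needs no assumed effect, for indexes of the kind checked here. On either reading no p-value results, and the beta-diversity distances are never compared between the groups.

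The cost relative to the plan's own taxon tests depends on the shape of the true difference. It is about nil for a concentrated one. Against a diffuse one it can be about half the power or more (28% v 53%, 35% v 91%), though less when the shift is strong (58% and 80% against 100% at factor 1.35). All these percentages rest on assumed numbers of taxa, effects and variability, on Wilcoxon tests with BH at 0.05, and on all 80 patients giving stool. They illustrate direction and do not predict this study's power.

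This is a worthwhile improvement to a secondary baseline comparison, not a serious defect. Whether to adjust for age and sex is a separate question of confounding, which this point neither raises nor settles.

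**What to change.** In the microbiome paragraph of section 4.2, replace the principal component clause with the following:
- Principal coordinates analysis of one named beta-diversity distance, for example Bray-Curtis.
- One prespecified PERMANOVA on that distance, aMCI against normal cognition, with a check of equal dispersion. Unequal spread can itself produce a significant result, particularly with 80 against 15 to 20.
- A direct comparison of the within-sample indexes between the groups.
- The genus and species comparisons with BH, kept as planned.

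Naming the distance in advance also prevents a choice among metrics after the results are seen. The cost is SAP wording, minor analysis work on diversity measures the plan already produces, and one more prespecified test on a secondary baseline comparison. No new data are needed.
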